15.3.1 Treatment Discontinuation

Treatment with study drug should be discontinued if any of the following occur:

- Development of accelerated hypertension (defined as systolic blood pressure ≥ 180 *and* diastolic blood pressure ≥ 100 mm Hg) that cannot be managed by the adjustment of concomitant medications such as antihypertensive medications.
- Development of congestive heart failure that cannot be managed by the adjustment of concomitant medications such as diuretics and antihypertensive medications.
- Development of diabetic signs/symptoms (ie, HbA1c $> 6.5\%$, or fasting plasma glucose > 126 mg/dL, or classic symptoms of hyperglycemia with random plasma glucose > 200 mg/dL) that cannot be managed by the adjustment of concomitant medications such as insulin and oral hypoglycemic agents.
- Flare or worsening of disease activity, defined as:
 - **Weeks 0 to 11:** DAS28-ESR ≥ 3.2 and increase of > 0.6 from the Week 0 assessment sustained over 2 consecutive study visits; **or** DAS28-ESR ≥ 3.2 and increased of > 1 from the Week 0 assessment at a single visit.
 - **Weeks 13 to 23:** DAS28-ESR < 3.2 and increase of 1.2 from the Week 12 assessment; **or** DAS28-ESR ≥ 3.2 and increased of > 0.6 from the Week 12 assessment sustained over 2 consecutive study visits; **or** DAS28-ESR ≥ 3.2 and increase of > 1 from the Week 12 assessment at a single visit.
- Failure to achieve LDA at Week 12.

- Development of any other AE of at least moderate intensity and possibly, probably or definitely related to study drug that cannot be managed by the adjustment of concomitant medications.

15.4 Storage of Clinical Supplies

Acthar and placebo will be maintained in a temperature controlled, secure locked area with restricted access at the study site.

Study drug will be supplied in kits containing the appropriate amount of vials according to the treatment group to which the subject is assigned. Study drug will be stored under refrigeration between 2° to 8°C (36° to 46°F). Please refer to the Pharmacy Manual for complete information regarding storage and accountability of study drug.

15.5 Drug Accountability

In accordance with ICH requirements, the investigator will, at all times, be able to account for all study drug furnished to the study site. A drug accountability record will be maintained for this purpose. The investigator must maintain accurate records indicating dates and quantity of study drug received, to whom it was dispensed (subject-by-subject accounting) and accounts of any study drug accidentally or deliberately destroyed. All unused study drug not involved in immediate subject dosing will be maintained under locked, temperature-controlled storage at the study site.

15.6 Compliance Monitoring

Prior to beginning the administration of study drug, subjects and/or their caregiver will be trained on dosing administration and must exhibit proper technique. Subjects and/or their caregiver will be trained on the completion of the study diary and will complete study diary entries to record all study drug administration and will bring it, along with all study drug kits including used vials to each visit. Each time study drug is dispensed compliance will be encouraged. Subject diary training is an ongoing process as the diary will be reviewed with the subject at each visit to monitor compliance with study drug administration.

16 SAFETY ASSESSMENTS AND PROCEDURES

The following safety assessments will be evaluated: AEs, physical examinations, clinical laboratory test results (chemistry, hematology, HbA1c, urinalysis, hepatitis serology, IGRA for TB test), and vital signs. All safety assessments will be performed at times outlined in the Schedule of Study Events (Table 7-1). Additional (unscheduled) safety assessments may be performed as needed.

16.1 Adverse Events

Adverse events will be recorded from signing of the ICF and followed by the investigator until the AE is resolved or stabilized. Any and all safety measures (which includes standard of care activities) should be provided by the study site to the subject. Any study site follow-up should be documented.

Refer to [Section 21](#) for additional details on the handling of AEs and SAEs.

16.2 Medical and Surgical History

Medical and surgical history will be obtained at the Screening Visit. Medical history will include a review of the following systems: general, dermatological, respiratory, cardiovascular, gastrointestinal, genitourinary, gynecological, endocrine, musculoskeletal, hematological, neuropsychological, immune (allergies), and head, eyes, ears, nose, and throat. Historical and current medical conditions including date of last menstrual period for female subjects will be recorded.

16.3 Current Medical Conditions

At each visit after screening, subjects will be asked about any changes in medical conditions, specifically new medical conditions and worsening of existing medical conditions. Any changes since the Screening Visit will be recorded as AEs, as appropriate.

16.4 Physical Examination

A complete physical examination will be performed at the Screening Visit and the Week 24/Early Termination Visit. The complete physical examination includes evaluation of the head, eyes, ears, nose, throat, neck (including thyroid), cardiovascular system (including assessment of heart, peripheral pulses, presence or absence of edema), lungs, abdomen (including liver and spleen, bowel sounds), lymph nodes, musculoskeletal system (including spine, joints, muscles) neurological system (including cranial nerves, reflexes, sensation, strength), skin, extremities and other conditions of note.

A limited physical examination, including evaluation of lungs, heart, abdomen, and extremities will be done at all other visits.

The findings of the physical examinations will be recorded. Any change from the Screening Visit physical examination that is considered clinically significant by the investigator will be recorded as an AE.

16.5 Height and Weight

Height will be collected at screening only. Weight will be collected at specified times during the study.

16.6 Vital Signs

Vital signs will be obtained after the subject has been seated for 5 minutes (minimum) and will include systolic and diastolic blood pressures, pulse rate, respiratory rate, and body temperature. Additionally, at the Screening and Baseline Visits, blood pressure will be measured at least 3 times, with 5 minutes between assessments after the subject has been seated for a minimum of 5 minutes prior to the initial blood pressure assessment.

The investigator may perform additional unscheduled vital sign measurements to evaluate or manage a suspected AE. These unscheduled vital sign measurements should be obtained after the subject has been seated for at least 5 minutes, if possible. Unscheduled vital signs will be recorded.

The date and time for all vital sign assessments will be recorded.

Screening/Baseline Assessments

A subject with systolic blood pressure > 140 mm Hg and diastolic blood pressure > 90 mm Hg (average of 3 assessments) at the Screening or Baseline Visits does not qualify for the study.

On Study Assessments

If an on-study vital sign is not in the site's standard reference range, an AE will be recorded if the investigator determines the change is clinically significant or requires a change in the subject's clinical management.

16.7 Clinical Laboratory Tests (Chemistry, Hematology, Urinalysis, HbA1c, Hepatitis Serology, IGRA, and Pregnancy Tests)

The clinical laboratory tests are listed in [Section 32.1](#). All clinical laboratory tests will be done at a central laboratory facility except urine pregnancy (at the site), and IGRA (local laboratory). Specific instructions for collection, processing, storage, and shipment of clinical laboratory samples will be provided in a separate laboratory manual, where appropriate.

Samples for laboratory testing at all visits may be collected under fasted or nonfasted conditions. The date and time of the sample collection must be documented on the laboratory report. Investigators must review and sign laboratory reports. The clinical significance of each

laboratory abnormality will be documented. New clinically significant laboratory abnormalities or clinically significant changes in laboratory values will be reported as AEs, as appropriate.

Hematology with differential, serum chemistry, other specific tests, and urinalysis samples will be collected at the specific times starting at screening and throughout the study.

In addition:

- All female subjects of child-bearing potential will have a serum pregnancy test at the Screening and Week 24/Early Termination Visits. Urine pregnancy tests will be done at all other visits throughout the study. Results must be available prior to dosing with protocol mandated study drug. Subjects with positive results will be ineligible for study entry (Screening Visit or Predose) or withdrawn from the study. Any female subject that becomes pregnant during the study will be immediately withdrawn and the pregnancy report as per [Section 21.6](#).

If applicable, the subject's agreement to use contraception throughout their study participation (through the Follow-up Visit) will be documented.

- HBsAg and HBcAb will be performed at the Screening Visit. Results of these tests must be negative or nonreactive for subjects to qualify for the study.
- HCV antibody testing will be performed at the Screening Visit. A positive HCV antibody will automatically trigger a HCV PCR analysis. HCV PCR must be < 25 IU/mL to qualify for the study.
- IGRA for TB will be performed at the Screening Visit. Results of this test must be negative for subjects to qualify for the study.
- HbA1c will be performed at the Screening Visit HbA1c must be $\leq 6.5\%$ for subjects to qualify for the study. Additional HbA1c tests will be done at specified times during the protocol.

Out-of-Range Laboratory Values

Laboratory values from samples collected at the Screening Visit will be evaluated by the investigator for eligibility of the subject in the study. Clinical laboratory tests may be repeated once to determine subject eligibility.

Laboratory values that fall outside the reference range from samples collected during the study or at study exit or early termination will be assessed by the investigator for clinical significance. If the out of range value for samples is deemed clinically significant by the investigator, an AE will be recorded.

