12 SELECTION OF SUBJECTS

12.1 Inclusion Criteria

Subjects must meet all of the following criteria for inclusion in the study at the Screening Visit and the Baseline Visit.

1. Subjects must be adequately informed and understand the nature and risks of the study and must be able to provide a signature and date on the ICF.
2. Subjects must be ≥ 18 years of age at Screening Visit and can be male or female.
3. Female subjects must be of nonchildbearing potential (history of hysterectomy, bilateral oophorectomy, or postmenopausal with no history of menstrual flow in the 12 months prior to the Screening Visit), or if of childbearing potential must be nonpregnant, nonlactating and agree to use effective contraception with a male partner throughout study participation (through the Follow-up Visit). Acceptable forms of contraception include hormonal measures (oral contraceptive pills, contraceptive patch, contraceptive ring, injections), intrauterine devices, double barrier method (condom plus diaphragm, condom or diaphragm plus spermicidal gel or foam), and abstinence.
4. Male subjects with a female partner of childbearing potential must have been surgically sterilized (vasectomy) or agree to use a double barrier method for contraception (condom plus diaphragm, condom or diaphragm plus spermicidal gel or foam) or remain abstinent throughout their study participation (through the Follow-up Visit).
5. Subjects must meet the criteria for RA as defined by the 2010 ACR/EULAR classification at the Screening Visit ([Aletaha et al, 2010](#)).
6. Subjects must have persistently active RA defined as a DAS28-ESR > 3.2 despite treatment with required biologic/nonbiologic DMARD(s) and a corticosteroid as defined below at the Screening and Baseline Visits.

7. Subjects must have been on a corticosteroid in the 12 weeks prior to the Screening Visit and on a stable dose of 5 mg to 10 mg of prednisone (or prednisone equivalent) for 4 weeks prior to the Screening Visit.
8. Subjects must have been on 1 of the following:
 - MTX \leq 20 mg per week and 1 additional allowed biologic or nonbiologic DMARD for at least 12 weeks prior to the Screening Visit and must remain on those doses throughout the study, OR
 - One allowed biologic DMARD for at least 12 weeks prior to the Screening Visit and must remain on that dose throughout the study.

Table 12-1 Allowed DMARDs

Allowed Nonbiologic DMARDs	Allowed Biologic DMARDs

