Sulfasalazine 2 to 3 g per day (QD)	Infliximab 3 to 10 mg/kg every 4 to 8 weeks
Leflunomide 20 mg QD	Adalimumab 40 mg every other week
Hydroxychloroquine (HDQ) up to 200 mg twice a day	Entanercept 50 mg per week
Tofacitinib 10 mg QD	Certolizumab 200 mg per week to 400 mg every 4 weeks (inclusive)
	Golimumab 50 mg per month
	Abatacept 125 mg/mL SC per week or 500 to 1,000 mg intravenously every 4 weeks

9. Subjects taking non-steroidal anti-inflammatory drugs must be on a stable dose for 4 weeks prior to the Screening Visit, and remain on a stable dose throughout study participation.
10. Subjects must have a mean systolic blood pressure \leq 140 mm Hg and a diastolic blood pressure of \leq 90 mm Hg determined by the average of 3 seated readings taken at least 5 minutes apart at the Screening and Baseline Visits.
11. Subjects must be able to communicate effectively with study personnel.
12. Subjects must be able and willing to follow all protocol requirements and study restrictions.
13. Subjects must be able and willing to return for all study visits.

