12.3 Screen Failure

Subjects will be allowed to repeat any single screening assessment/procedure once, if necessary, if it is within the screening window. The subject will not be considered a screen failure unless the repeat assessment/procedure results do not meet eligibility criteria. The period from starting screening related procedures at the Screening Visit to the Baseline Visit must not exceed 28 days, inclusive of any repeat screening procedures.

Subjects who do not meet all of the eligibility criteria at the Screening or Baseline Visits will be deemed a screen failure and the reason for the screen failure will be documented. A subject who is a screen failure at the Screening or Baseline Visit may be rescreened. The subject must repeat all screening procedures. The period from the start of rescreening related procedures to the first dose of study drug must not exceed 28 days. Subjects may be rescreened only once.

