14.2 Baseline Visit (Week 0) and First Dose Procedures/Assessments

Predose evaluations will occur prior to the first dose of study drug.

The investigator or designee will complete the following procedures predose:

- Inclusion/exclusion criteria review; subject must meet all eligibility criteria at screening and baseline.
- Efficacy Questionnaires: General Health (VAS), Patient Assessment of Pain (VAS), Patient Global Assessment of Disease Activity (VAS), Patient Assessment of Physical Function assessed using the Health Assessment Questionnaire- Disability Index [HAQ-DI]), Functional Assessment of Chronic Illness Therapy- Fatigue Scale (FACIT-F) and Physician Global Assessment of Disease Activity (VAS).
- Work Productivity and Activities Impairment (WPAI).
- Current medical condition review.
- Limited physical examination.
- 28 Joint Count.
- Weight.
- Vital signs.
- Clinical laboratory tests.
- ESR and CRP.
- Urine pregnancy test.
- Vectra Disease Activity (Vectra[®] DA) sample.

- Serum and urine samples for [REDACTED]
[REDACTED]
[REDACTED]
[REDACTED] and urine creatinine.
- Subject diary training.
- Contact IXRS and confirm disease activity eligibility.
- Dispense study drug kits.
- Study drug administration under supervision of study staff and observation for at least 1 hour thereafter. Administration of all other doses will be done at home by the subject/caregiver.
- Adverse events and concomitant medications.

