15.1 Methods of Assigning Subjects to Treatment Groups

The investigator or designee will contact IXRS to register subjects at screening. The subject's identification (ID) number will be determined by the IXRS and will be used to identify the subjects for the duration of the study within all systems and documentation. Subject identification numbers will consist of 7 digits: [REDACTED]

A subject ID number will not be assigned to more than 1 subject. If a subject is not eligible to receive treatment, or should a subject discontinue from the study, the subject ID number cannot be reassigned to another subject.

In the event that a subject is rescreened within the screening window, they do not need a new subject ID number. At Baseline, qualified subjects who meet all of the eligibility criteria will be enrolled into the study.

The investigator or designee must contact the IXRS to report subjects as a screen failure if the subject does not meet eligibility criteria predose.

The investigator or designee must contact IXRS to record each subject visit, to receive the study drug kit assignments, and to report any subject status changes. At visits where it is required, components of the DAS28-ESR (swollen joint count, tender joint count, ESR, General Health VAS) will be entered at into IXRS and the DAS28-ESR will be calculated.

The investigator must maintain a subject master log linking the subject ID to the subject's name. The investigator must follow all applicable privacy laws in order to protect a subject's privacy and confidentiality. Information that could identify a subject will be masked on material received by the sponsor.

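### Section 16.6 disqualifies only subjects with both blood pressures raised, whereas inclusion criterion 10 is failed by either one

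*Combined protocol and SAP*

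**What the plan says.** The blood pressure entry limit is stated twice in the current text.

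- **Section 12.1, inclusion criterion 10**, states who qualifies: "Subjects must have a mean systolic blood pressure \leq 140 mm Hg and a diastolic blood pressure of \leq 90 mm Hg". The same item bases both values on an average of three seated readings at each of the two entry visits.
- **Section 16.6, Screening/Baseline Assessments**, states who does not, naming "A subject with systolic blood pressure > 140 mm Hg and diastolic blood pressure > 90 mm Hg". It applies the same three-reading average, and a subject who meets that description at either of the two entry visits is ruled out.

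Four other places bear on which statement governs:

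- Section 12.1, opening sentence: "Subjects must meet all of the following criteria for inclusion in the study at the Screening Visit and the Baseline Visit".
- Section 12.3: "Subjects who do not meet all of the eligibility criteria at the Screening or Baseline Visits will be deemed a screen failure".
- Section 14.2, predose check: "subject must meet all eligibility criteria at screening and baseline".
- Section 15.1: "qualified subjects who meet all of the eligibility criteria will be enrolled into the study".

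**The concern.** The two statements are meant to be complements, one describing who may enter and the other who may not, but they do not partition subjects in the same way. A subject with only one raised value fails criterion 10 and is not mentioned in Section 16.6.

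A site could plausibly take Section 16.6 at its word. It holds the measurement procedure, it has its own heading for screening and baseline, and it ends in a statement about qualifying. Elsewhere the protocol does use *and* between systolic and diastolic thresholds to mean that both must be exceeded: the accelerated hypertension stopping rule in Section 15.3.1 and the special-interest definition in Section 21.5 both do so, with the word emphasised. By contrast, the eligibility restatements in Section 16.7 for hepatitis B, hepatitis C, the TB assay and HbA1c all agree with exclusion criterion 20.

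What is at stake is a safety entry limit. Section 9.5 lists elevation of blood pressure among the most common reactions to Acthar, and Section 11.4 expects about 100 sites to apply the rule. A misreading would expose a subject the limit was meant to keep out and would create an avoidable eligibility deviation.

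**Working it through.** No sample size, power or alpha figure is involved, so the check is one of logic. Write S and D for the averaged systolic and diastolic pressures in mm Hg.

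**Inputs.** Limits of 140 and 90, the three-reading average, and the Screening and Baseline Visits are common to criterion 10 and Section 16.6.

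**Step 1: the two rules.**

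- Criterion 10 met: (S ≤ 140 and D ≤ 90) at Screening and at Baseline.
- Criterion 10 failed, by negation: (S > 140 **or** D > 90) at Screening **or** Baseline.
- Section 16.6 as written: (S > 140 **and** D > 90) at Screening **or** Baseline.

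Negating criterion 10 requires both connectives to change. Section 16.6 changes the one between the visits and leaves the one between the limits.

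**Step 2: single-visit cases.**

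| Reading | Criterion 10 | Named by 16.6 as written | Named if *or* is used |
|---|---|---|---|
| 135/85 | met | no | no |
| 150/85 | failed | no | yes |
| 135/95 | failed | no | yes |
| 150/95 | failed | yes | yes |
| 140/90 | met | no | no |
| 141/90 | failed | no | yes |
| 140/91 | failed | no | yes |
| 141/91 | failed | yes | yes |

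Of the three failing patterns (systolic only, diastolic only, both), Section 16.6 names 1 and leaves 2 unnamed. With *or* it names all 3.

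**Step 3: both visits together.** Each visit has four possible patterns (neither raised, systolic only, diastolic only, both), giving 4 × 4 = 16 combinations.

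- Failing criterion 10: all except neither raised at both visits, 16 − 1 = 15.
- Named by Section 16.6 as written: at least one visit with both raised, 16 − (3 × 3) = 7.
- Failing but unnamed: 15 − 7 = 8.
- Named with *or*: 16 − (1 × 1) = 15, which is every failing combination.

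These are counts of logical cases, not of patients. The documents give no blood pressure distribution, so no proportion of subjects can be derived from them.

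**The case against.** The strongest reply is that the two sentences do not conflict. Everyone whom Section 16.6 rules out also fails criterion 10. Section 16.6 gives one sufficient reason for not qualifying; it does not say that it is the only reason, and it nowhere says that 150/85 qualifies. A site can obey both. This stands, and it is why Section 16.6 is better called an incomplete restatement than a contradictory rule.

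It is also true that the protocol already settles which text governs. Sections 12.1, 12.3, 14.2 and 15.1 all require every criterion to be met, and Table 7-1 schedules the criteria review at both Screening and Baseline. For harm to follow, a site would have to rely on Section 16.6 and miss criterion 10 at those reviews. Exclusion 11 (uncontrolled hypertension), exclusion 21 (investigator judgment) and the withdrawal rules in Section 22.1 give further protection, and blood pressure is measured at every visit. This stands as a reason for low weight. It does not make the sentence right: exclusion 11 gives no blood pressure figure and exclusion 21 rests on opinion, so neither replaces the numeric limit.

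Finally, nothing in the primary endpoint, the Part 2 comparison or the analysis population definitions depends on this sentence. That is agreed.

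**Conclusion.** The point holds as a low-severity wording error. Section 16.6 is narrower than the criterion it restates: it covers 1 of the 3 single-visit failing patterns, and 7 of the 15 failing combinations across two visits. The intended rule is not in doubt, because criterion 10 governs. The practical risk is confined to a site relying on Section 16.6 when it enrols; the number of subjects affected is unknown and may be zero. There is no effect on alpha, power or the efficacy analyses.

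The conclusion assumes only that *and* in Section 16.6 carries its ordinary meaning, as it does between the blood pressure thresholds in Sections 15.3.1 and 21.5. That the wording is a drafting slip is an inference from the half-completed negation; the mismatch exists whether or not that inference is right.

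**What to change.** In Section 16.6, replace *and* with *or* between the two limits, so that a three-reading average above 140 mm Hg systolic or above 90 mm Hg diastolic, at either visit, disqualifies. Alternatively, delete the sentence and refer to inclusion criterion 10, which leaves a single statement of the rule.

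The cost is one word or one cross-reference in the next amendment, with no change to design, sample size or analysis.
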